7.6 Baseline Descriptive Statistics

Descriptive statistics will be utilized to summarize the demographic and baseline data.

For continuous endpoints, descriptive statistics will be presented, including the number of participants with the measurement, mean, standard deviation, median, minimum and maximum. For categorical endpoints, descriptive statistics will include the number with the event or characteristic, the number evaluated and the percentage presented.

7.7 Tabulation of Individual participant Data

Listings of the primary and secondary endpoints will be presented by patient and by time point for each treatment.

7.8 Exploratory Analyses

Any exploratory analyses will use the both ITT and PP populations for analysis.

8 Data Management

8.1 Data Collection and Management Responsibilities

Data collection is the responsibility of the clinical trial staff at the site under the supervision of the site investigator. The investigator is responsible for ensuring the accuracy, completeness, legibility, and timeliness of the data reported. Data will be captured using applicable CDASH data element standards.

All source documents should be completed in a neat, legible manner to ensure accurate interpretation of data.

Hard copy worksheets may be provided for use as source document worksheets for recording on-site participant data. Data recorded in the electronic case report form (eCRF) derived from source documents should be consistent with the data recorded on the source documents.

All clinical data (including applicable patient diary entries) shall be entered into a 21 CFR Part 11 compliant data system provided by a qualified data management vendor. Such a system will

include password protection and internal quality checks, such as automatic range checks, to identify data that appear inconsistent, incomplete, or inaccurate. Data handling, cleaning and analysis shall be performed per Standard Operating Procedures by a qualified vendor. Missing or erroneous data anomalies will be communicated to the site(s) for clarification and correction.

8.2 Study Records Retention

Investigational centers shall retain all study records for a minimum of three years from the date of Federal Financial Report submission, or for up to 7 years from the date of product market clearance. No records will be destroyed without the written consent of the Sponsor. The Sponsor shall inform the study sites when the study records are no longer needed to be retained.

8.3 Confidentiality and Privacy

Participant confidentiality and privacy is strictly held in trust by the participating investigators, their staff, and the sponsor(s) and their interventions. This confidentiality is extended to cover testing of biological samples in addition to the clinical information relating to study participants. Therefore, the study protocol, documentation, data, and all other information generated will be held in strict confidence. No information concerning the study or the data will be released to any unauthorized third party without prior written approval of the Sponsor. All research activities will be conducted in as private a setting as possible.

All data obtained in the context of clinical trial are subject to data protection. The subject's name in addition to other data related to persons (excluding date of birth/age, and gender) are not to be disclosed by the investigator.

Study participant research data, which is for purposes of statistical analysis and scientific reporting, will be transmitted to and stored at the Sponsor. This will not include the participant's personal contact or identifying information. Rather, individual participants and their research data will be identified by a unique study identification number. The study data entry and study management systems used by clinical sites and by Sponsor research staff will be secured and password protected. At the end of the study, all study databases will be de-identified and archived at the Sponsor.

8.4 Future Use of Stored Specimens and Data

Data collected for this study will be analyzed and stored at the Sponsor or a qualified third party data management vendor. After the study is completed, the de-identified, archived data will be transmitted to and stored at the Sponsor, for use by other researchers including those outside

of the study. Permission to transmit data to the Sponsor will be included in the informed consent.

All study data remain the property of the study Sponsor.

9 Amendments

All protocol changes, modifications or amendments shall be initiated by the Sponsor and documented in writing. The Sponsor shall notify the Principal Investigators and submit changes for applicable regulatory authority for review. IRB/Ethics approval of the protocol changes must be received by Sponsor in writing before any change may be implemented at the study sites.

Withdrawal of IRB/Ethics approval must be submitted to Sponsor within five (5) business days of the change.

10 Deviations

A protocol deviation is any noncompliance with the clinical trial protocol, GCPs, study manual, monitoring or analysis plans. The noncompliance may be either on the part of the participant, the investigator, or the study site staff. As a result of deviations, corrective actions are to be developed by the site and implemented promptly.

Deviations shall be reported by the study site or study monitor to the Sponsor or qualified designee. Protocol deviations shall be sent to the reviewing Institutional Review Board (IRB) or local Ethics Committee per review board policy and/or to the Sponsor and IRB/Ethics Committee within 10 working days of knowledge of the event. These practices are consistent with ICH E6 GCP and 21 CFR Parts 50 and 56.

11 Device Accountability

Access to the investigational device shall be controlled and the Achilles infusion set shall be used only in this clinical investigation and according to the Clinical Investigation Plan presented here.

Capillary Biomedical, Inc. shall keep records to document the physical location of all investigational devices from shipment of investigational devices to the investigation sites until return or disposal.

The principal investigator or an authorized designee shall keep records documenting the receipt, use, return and disposal of the investigational devices, which shall include

- a) the date of receipt,

- b) identification of each investigational device (batch number/serial number or unique code),
- c) the expiry date, if applicable,
- d) the date or dates of use,
- e) participant identification,
- f) date on which the investigational device was returned/explanted from subject, if applicable, and
- g) the date of return of unused, expired or malfunctioning investigational devices, if applicable.

12 Statements of Compliance

12.1 Declaration of Helsinki

This study will be conducted in accordance with the ethical principles of the Declaration of Helsinki (64th WMA General Assembly, Fortaleza, Brazil, October 2013).

12.2 Standards and Regulations

This study will be conducted in compliance with this protocol, ISO 14155, designated Standard Operating Procedures, and with local laws and regulations relevant to the use of new medical devices in Australia.

12.3 Ethics Committee Approval

The clinical investigation proposed here shall not begin until the required approval from the local Ethics Committee and/or regulatory authority have been obtained.

12.4 Insurance

The study is sponsored and funded by Capillary Biomedical, Inc. Costs necessary to perform the study will be agreed upon prior to study start. Capillary Biomedical will arrange with the local sponsor for subject insurance for all participating participants. The investigators shall receive a copy of the insurance certificate and the insurance conditions. The latter must be known to the participants and made available on request.

13 Informed Consent Process

13.1 General

Informed consent shall be obtained in writing from the subject and the process shall be documented before any procedure specific to the clinical investigation is applied to the subject.

13.2 Process of Obtaining Informed Consent

The general process for obtaining informed consent shall be documented in the CIP and shall

- a) ensure that the principal investigator or his/her authorized designee conducts the informed consent process,
- b) include all aspects of the clinical investigation that are relevant to the subject's decision to participate throughout the clinical investigation,
- c) avoid any coercion or undue improper influence on, or inducement of, the subject to participate,
- d) not waive or appear to waive the subject's legal rights,
- e) use native non-technical language that is understandable to the subject,
- f) provide ample time for the subject to read and understand the informed consent form and to consider participation in the clinical investigation,
- g) include personally dated signatures of the subject and the principal investigator or an authorized designee responsible for conducting the informed consent process,
- h) provide the subject with a copy of the signed and dated informed consent form and any other written information, and
- i) ensure important new information is provided to new and existing participants throughout the clinical investigation.

14 Adverse Events

14.1 Definition of Adverse Events

An Adverse Event (AE) is defined any untoward medical occurrence associated with the use of an intervention in humans, whether or not considered intervention-related (21 CFR 312.32 (a)).

Investigational device adverse events/effects shall be reported as anticipated or unanticipated per 21 CFR 812.3, and drug reactions and/or adverse drug effects shall be reported as described in CFR 312.32. Events shall be reported to the Sponsor per protocol and to the governing IRB per IRB requirements and all applicable study regulations.

A list of anticipated (expected) adverse effects related to the study device, study intervention or testing procedures and known complications of diabetes disease, insulin use, treatments and treatment equipment have been provided in reference document 150-1072-02 Feasibility Study Anticipated Adverse Event Definitions.

14.2 Adverse Device Effect (ADE)

All device deficiencies related to the identity, quality, durability, reliability, safety or performance of an investigational medical device shall be documented throughout the clinical investigation and appropriately managed by the sponsor.

14.3 Serious Adverse Event (SAE)

A Serious Life-threatening Adverse Event or Life-threatening Suspected Adverse Reaction is defined as an adverse event/effect or suspected effect that is considered "life-threatening" that if, in the view of either the investigator or sponsor, its occurrence places the patient or subject at immediate risk of death.

A serious adverse event or serious suspected adverse reaction - defined as an adverse event or suspected adverse reaction is considered "serious" if, in the view of either the investigator or sponsor, it results in any of the following outcomes:

- death,
- a life-threatening adverse event,
- inpatient hospitalization or prolongation of existing hospitalization,
- a persistent or significant incapacity or substantial disruption of the ability to conduct normal life functions, or
- a congenital anomaly/birth defect.

The Principal Investigator or, at the direction of the Principal Investigator, study personnel will complete a serious adverse event (SAE) report and provide the information to the US and local sponsor contacts within 1 working day of the occurrence of the SAE. The Principal Investigator will inform the Ethics Committee of any Serious Adverse Events.

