1.4.3 Exclusion Criteria

Participants who meet any of the following criteria will be excluded from study participation:

- 1) Participants whose average total daily insulin dose exceeds 85 units/day (i.e. typically change insulin reservoirs more often than every 3.5 days on average)
- 2) Participants who routinely change their commercial insulin infusion sets twice weekly or less often (wear time $>$ 3.5 days)
- 3) Female participant is pregnant or nursing¹
- 4) Participant has abnormal skin at intended device infusion sites (existing infection, inflammation, burns, or other extensive scarring)
- 5) Participant has HbA1C $>$ 8.5% at screening
- 6) Participant has documented history in last 6 months of severe hypoglycemia associated with cognitive dysfunction sufficiently severe to require third party intervention or a history of impaired awareness of hypoglycemia.
- 7) Participant has a history of diabetic ketoacidosis in the last 6 months
- 8) Participant has known cardiovascular disease considered to be clinically relevant by the investigator
- 9) Participant has known arrhythmias considered to be clinically relevant by the investigator
- 10) Participant has known history of:
 - a) Cushing's Disease,
 - b) pancreatic islet cell tumor, or
 - c) insulinoma

¹ Documented negative pregnancy test results for female participants required unless participant is menopausal without any spontaneous menstrual cycles for $>$ 12 months or key organs have been removed.

- 11) Participant has:
 - a) Lipodystrophy,
 - b) extensive lipohypertrophy, as assessed by the investigator
- 12) Participant is undergoing current treatment with:
 - a) Systemic oral or intravenous corticosteroids,
 - b) monoamine oxidase (MAO) inhibitors,
 - c) non-selective beta-blockers,
 - d) growth hormone,
 - e) thyroid hormones, unless use has been stable during the past 3 months
- 13) Subject has significant history of any of the following, that in the opinion of the investigator would compromise the subject's safety or successful study participation:
 - a) Alcoholism,
 - b) drug abuse
- 14) Significant acute or chronic illness, that in the investigator's opinion, might interfere with subject safety or integrity of study results
- 15) Planned operation, MRI or CT which require removal of infusion set or CGM sensor during wear periods
- 16) Current participation in another clinical drug or device study
- 17) AST and ALT >120 U/L
- 18) Creatinine \geq 1.8 mg/dL

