4.4 Risks of Participation

This study includes T1DM participants that undergo routine diabetes treatment and glucose control methodology. A standardized study protocol, case report forms, study and investigational device use training will be provided to all study investigators/staff and study participants prior to any study related intervention or testing.

The study population consists of adult volunteer participants who have been diagnosed with T1DM, and have used an insulin pump for at least 6 months for basal and bolus insulin therapy to control their blood glucose. T1DM diagnosis will be confirmed at screening by c-peptide lab test.

Only insulin pump users with at least 6 months of experience with pump therapy will be enrolled to minimize the risk of pump use errors. Each potential study subject will be required to submit a minimum of 14 days of pump data to confirm pump use compliance. Patients who routinely wear their infusion set for >3.5 days will be excluded from participation to ensure a homogenous patient population of participants who adhere to infusion set labeling restrictions. Screening including physical exam, ECG and laboratory testing will rule out patients with anemia or known cardiovascular disease who may be at greater risk of procedure-induced anemia or whose hypoglycemia symptoms may be masked by concomitant medication.

The primary risks associated with extended wear of the Achilles infusion set are increased risk of hyperglycemic or hypoglycemic episodes and/or infusion site irritation or infection. To ensure patient safety while using the newly developed infusion sets, patients are required to wear a CGM sensor throughout the study. Only participants with previous CGM experience and willingness to wear a CGM will be recruited. The Dexcom G5 CGM should be set with alarm systems engaged throughout study duration. Study staff will be able to monitor each patient's interstitial glucose remotely and will be notified via text in case of alarm. Participants will be instructed to contact their study site for any issues.

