6.4 Monitoring Plan

6.5.1 Safety Oversight

Unanticipated Adverse Device Effects and Serious Adverse Events will be reported to the Sponsor within 24 hours of knowledge of the event. Sponsor shall endeavor to review such events within 24 hours of notification. Preliminary event seriousness and device relationship will be assessed by the principal investigator or a qualified designee.

A qualified clinician shall act as the study Medical Monitor. Adverse events shall be reviewed at least monthly by Sponsor and/or Medical Monitor. Serious or unanticipated adverse events shall be reviewed upon receipt of full documentation of the event, including any sequelae and treatment required for resolution. The Medical Monitor will document event review and adjudication.

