14.8 Unanticipated Adverse Device Effect (UADE)

An unanticipated adverse device effect is defined as “any serious adverse effect on health or safety or any life-threatening problem or death caused by, or associated with, a device, if that

effect, problem, or death was not previously identified in nature, seriousness, , or degree of incidence in the investigational plan or application (including a supplementary plan or application), or any other unanticipated serious problem associated with a device that relates to the rights, safety, or welfare of participants.”

For consideration of device safety and performance, an unanticipated adverse event is an event that has not been described in the investigational plan, study protocol, attachments, Instructions for Use, product labeling, or other product descriptions including those of ancillary study products.

A UADE must be directly related to the device under investigation.

The Sponsor is responsible for promptly reviewing any and all information relevant to the device or drug product and considering the impact of the all adverse event (s) on study continuation.

Unexpected Adverse Event or Unexpected Suspected Adverse Reaction

An unexpected adverse event/effect is defined as an adverse event or suspected adverse reaction is considered "unexpected" if it is not listed in the investigator brochure or is not listed at the specificity that has been observed; or, if an investigator brochure is not required or available, is not consistent with the risk information described in the general investigational plan or elsewhere in the current application, as amended.

15 Vulnerable Population

Individuals whose willingness to volunteer in a clinical investigation could be unduly influenced by the expectation, whether justified or not, of benefits associated with participation or of retaliatory response from senior members of a hierarchy in case of refusal to participate are considered vulnerable. This study is designed so that only adult patients in full control of their disease may participate (i.e. non-vulnerable populations).

16 Termination

Each subject's participation in the clinical study will be terminated following the post- monitoring examination or when all adverse events have been resolved. Prior to this time, the subject may voluntarily withdraw at any point in the study or the Investigator and/or CapBio may determine that it is in the best interests of the subject to be removed from the study.

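### Ketoacidosis or third-party-assisted hypoglycemia treated without admission is not automatically serious under 14.3 and can fall outside expedited reporting; separately, 14.8 contradicts its own UADE definition

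*Combined protocol and SAP*

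**What the plan says.** **Expedited route.** Section 6.5.1 states: "Unanticipated Adverse Device Effects and Serious Adverse Events will be reported to the Sponsor within 24 hours of knowledge of the event". Adverse events in general are reviewed by the sponsor and/or Medical Monitor at least once a month.

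**Seriousness.** Section 14.3 lists five outcomes, assessed by either the investigator or the sponsor: death; a life-threatening event, meaning immediate risk of death; "inpatient hospitalization or prolongation of existing hospitalization"; incapacity that is persistent or significant, or substantial disruption of normal functioning; and congenital anomaly. There is no general criterion for a medically important event or for an intervention that averts a worse outcome. Neither ketoacidosis nor severe hypoglycemia is named.

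**The trial's own harms.** Section 4.4 says: "The primary risks associated with extended wear of the Achilles infusion set are increased risk of hyperglycemic or hypoglycemic episodes", alongside site irritation or infection, and 5.5 repeats this. Section 3.1 lists ketoacidosis among the dangerous complications of unreliable absorption. Exclusion 6 bars anyone with recent "severe hypoglycemia associated with cognitive dysfunction sufficiently severe to require third party intervention". Exclusion 7 reads: "Participant has a history of diabetic ketoacidosis in the last 6 months". Section 3.3 records that the cannula has never delivered insulin in humans.

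**UADE and SADE.** Section 14.8 defines a UADE as a serious, not previously identified effect "caused by, or associated with, a device", and later adds: "A UADE must be directly related to the device under investigation". For a SADE, 14.4 accepts an event that is either related to or associated with the device.

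**Tabulation.** Section 7.5 summarizes adverse events by seriousness and by relationship to the device, not by severity.

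**The concern.** In a first insulin use of a 7-day infusion set, ketoacidosis and assisted hypoglycemia are the clinical events that say most about failed or erratic delivery. The protocol regards a recent history of either as reason enough to keep a person out. Yet if one occurs on study and the participant is not admitted, nothing in the text makes it an expedited report. Whether the sponsor hears on the SAE clock, and whether the event appears in the serious rows of the safety tables, depends on a case-by-case judgement. With 20 participants, one such judgement changes the serious-event table.

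**Working it through.** The protocol states no figure on this point, so the check is to walk cases through the text.

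**1. Two cases against 14.3.** Case A is ketoacidosis treated in an emergency department, with discharge home. Case B is hypoglycemia with cognitive dysfunction reversed by a relative at home.

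| 14.3 outcome | Case A | Case B |
|---|---|---|
| Death | no | no |
| Immediate risk of death | by judgement | by judgement |
| Inpatient admission or prolongation | no | no |
| Incapacity or substantial disruption | by judgement | by judgement |
| Congenital anomaly | no | no |

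No row is met automatically. The severity scale in 14.5 counts temporary incapacity as severe, but 14.3 does not link that grade to seriousness.

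**2. Other routes if the event is judged non-serious.** A SADE (14.4) needs a consequence characteristic of an SAE, so it falls away. A UADE (14.8) must be serious and not previously identified. Section 14.8 gives no separate seriousness list, and hyper- and hypoglycemic episodes are already named in 4.4 and 5.5. The event fails there before the relationship wording is reached. Only the general review remains, with its minimum monthly frequency.

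**3. Effect on the tables.** Suppose one such event among the 20 participants in 6.2.6. This is an assumption, because the documents give no rate. Per-subject incidence is 1/20 = 5%. Judged serious, the serious row shows 1/20 = 5%; judged non-serious, it shows 0/20 = 0%. The event still appears among the non-serious events, but 7.5 gives it no line of its own.

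**4. Relationship wording.** Three passages differ:
- 14.8, definition: caused by or associated with the device.
- 14.8, later sentence: directly related.
- 14.4: related to or associated with the device.

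The categories in 14.6 include no direct relationship; its related class accepts a reasonable possibility or a temporal link. A serious, unidentified event could therefore be related under 14.6 and a SADE under 14.4, yet be refused as a UADE under the later sentence of 14.8.

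**5. SAE clocks.** Section 6.5.1 runs 24 hours from knowledge. Section 14.3 asks for a report "within 1 working day of the occurrence of the SAE". Neither is uniformly stricter. For an event that occurs and is known on a Friday evening, 6.5.1 expires on Saturday evening, while 14.3 allows until the next working day. For an event on a Monday first reported to the site on Thursday, 14.3 has expired before the site knew, while 6.5.1 runs to Friday.

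**The case against.** **Judgement can catch these events.** Either the investigator or the sponsor may classify the event as serious, and the incapacity criterion says persistent or significant. Hypoglycemia with cognitive dysfunction that needs another person's help can reasonably be called significant incapacity. This stands: the events can miss the route; they do not necessarily miss it. Admitted cases are caught.

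**Other documents may cover it.** Section 14.1 refers to a separate document of anticipated adverse event definitions (150-1072-02), and 12.2 cites ISO 14155. Their text is not available here, so coverage there cannot be excluded. However, 14.1 describes the former as a list of anticipated effects, not as seriousness criteria, and 14.3 does not refer to it.

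**Participants are monitored closely.** Staff receive remote CGM alarms, there is a 24/7 helpline, participants must contact staff early after set failure, and Week 3 depends on an untroubled Week 2. Hyperglycemia above 250 mg/dL with ketones of at least 0.6 mmol/L and no intercurrent illness is also a primary-endpoint failure, listed by patient under 7.7. This stands as protection and as data capture. None of it creates a timed report to the sponsor.

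**Stronger readings to avoid.**
- A reader might infer that the decision on study continuation would rest on an incomplete set of events. Section 14.8 says otherwise: the sponsor must promptly review all relevant information and weigh all adverse events, not only serious ones.
- A reader might infer that the sponsor would learn of such an event about 30 days late. Monthly is a minimum review frequency in 6.5.1, not a notification deadline, so no delay of that length follows.
- A reader might infer that the direct-relationship sentence is what keeps these events off the UADE route. They fail earlier, as non-serious or already identified. The sentence is a separate inconsistency.

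**Conclusion.** The point holds in limited form. Under 14.3 as written, ketoacidosis or third-party-assisted hypoglycemia treated without admission is serious only by judgement. It can therefore fall outside the expedited report in 6.5.1 and be counted as non-serious in 7.5, and neither the SADE nor the UADE route restores it. The internal conflict in 14.8, and its conflict with 14.4, is real but secondary. So is the mismatch between the two SAE clocks.

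The size cannot be estimated, because the documents give no rate for these events; 5% against 0% for one event in 20 participants is illustrative only. The conclusion assumes that the documents cited in 14.1 and 12.2 add no overriding seriousness rule. It supports a worthwhile wording change. It does not show that the safety conclusion or the continuation decision is unsound.

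**What to change.** 1. In 14.3 and 6.5.1, name diabetic ketoacidosis and hypoglycemia requiring third-party intervention, in the terms already used in exclusions 6 and 7, as events always reported to the sponsor on the SAE timeline wherever they are treated. This concerns reporting only and changes nothing in clinical management. If document 150-1072-02 already does this, cite it at both places.
2. In 7.5, show these two events on a separate line, whatever their seriousness classification.
3. In 14.8, delete the sentence that demands a direct relationship, so that the definition in the same section governs, in line with 14.4.
4. Reconcile the SAE clocks in 6.5.1 and 14.3 into one rule with one starting point.

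The cost is protocol and adverse-event form wording, through the amendment process in section 9. The downside is possibly a few more expedited reports.
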